7.7.3 Romidepsin Dose Modifications

If toxicity, in the opinion of the investigator, is attributable to Romidepsin, the guideline for Romidepsin dose modification should be followed. Final discretion is with the treating investigator in regards to aggressive dose reductions, as well as the number of dose reductions.

7.7.3.1 Hematologic Toxicity

- Grade 3 or 4 neutropenia or thrombocytopenia: Treatment with romidepsin should be delayed until the specific cytopenia returns to ANC $\geq 1.5 \times 10^9/L$ and platelet count $\geq 75 \times 10^9/L$ or baseline, then therapy may be restarted at same dose.
- Grade 4 febrile ($\geq 38.5^\circ C$) neutropenia or thrombocytopenia that requires platelet transfusion: Treatment with romidepsin should be delayed until the specific cytopenia returns to \leq Grade 1 or baseline, and then the dose should be permanently reduced to 10 mg/m^2 or lower dose.

7.7.3.2 Non-Hematologic Toxicities

Nonhematologic toxicities except alopecia

- Grade 2 or 3 toxicity: Treatment with romidepsin should be delayed until toxicity returns to \leq Grade 1 or baseline, then therapy may be restarted at same dose. If Grade 3 toxicity recurs, treatment with romidepsin should be delayed until toxicity returns to \leq Grade 1 or baseline and the dose should be permanently reduced to 10 mg/m^2 or lower.
- Grade 4 toxicity: Treatment with romidepsin should be delayed until toxicity returns to \leq Grade 1 or baseline, then the dose should be permanently reduced to 10 mg/m^2 or lower dose.
- Romidepsin should be discontinued if Grade 3 or 4 toxicities recur after dose reduction.

8 ASSESSMENT OF EFFICACY

8.1 Specification of the Efficacy Parameters

Evaluable for objective response: Patients who have had a pre-treatment baseline efficacy evaluation and at least one post-treatment efficacy evaluation will be considered evaluable for response. “**Investigator assessed response**” will be used in the study. These patients will have their response classified according to the definitions stated below.

Disease parameters:

- **Measurable disease:** Measurable lesions are defined as those that can be accurately measured in at least two dimensions with conventional techniques (PET/CT, MRI, x-ray) or as $>1.5 \text{ cm}$ with spiral CT scan. All tumor measurements should be recorded in centimeters.
- **Non-measurable disease (evaluable disease):** All other lesions (or sites of disease) including small lesions, ($<1 \text{ cm}$ using spiral CT scan) are considered non-measurable disease. Bone lesions, leptomeningeal disease, ascites, pleural/pericardial effusions, lymphangitis, and cystic lesions are all non-measurable.
- **Target lesions:** All measurable lesions up to a maximum of 6 lesions total, representative of all involved organs, should be identified as target lesions and recorded and measured at baseline.

Target lesions should be selected on the basis of their size (lesions with the longest SPD diameter), and the highest SUV avidity (high SUV lesions may be prioritized even if not the largest lesions, and their suitability for accurate repeated measurements (either by imaging techniques or clinically). A baseline sum of the diameters (longest for non-nodal lesions, short axis for nodal lesions) for all target lesions will be calculated and reported as the baseline sum diameters. The baseline sum of the diameters will be used as reference to further characterize any objective tumor regression in the measurable dimension of the disease.

- **Non-target lesions:** All other lesions (or sites of disease) including any measurable lesions over and above the 6 target lesions should be identified as non-target lesions and should also be recorded at baseline. Measurements of these lesions are not required, but the presence, absence, or in rare cases unequivocal progression of each should be noted throughout follow-up.

Evaluation of best objective response: The best objective response is the best response recorded from the start of the treatment until disease progression/recurrence.

8.2 Response Evaluations and Measurements

In all patients (PTCL and CTCL), the response will be assessed approximately at 8 weeks interval for the first two assessments [(e.g. C3D1 (\pm 7 days), C5D1 (\pm 7 days)] and then at C8D1 (\pm 7 days) and/ or at the EOT or as clinically indicated (if clinical progression is suspected).

- **PTCL**

PTCL patients will be evaluated according to Lugano classification Cheson 2014)^[16] ([Appendix C](#)) using the CT scan. PET-CT will be preferred for FDG-avid lymphomas. The modality chosen should be the same throughout the duration of the study. In addition, PET-CT will be performed at C3D1 (\pm 7 days) and to confirm CR. If PET and CT scan at Screening are negative for disease involvement in the neck, subsequent CT scans may not include neck. If PET and CT scans at Screening are positive for disease involvement of the neck, subsequent CT scans must include neck. Disease assessments and imaging should not be delayed for delays in cycle starts. Disease assessments and imaging should be continued until documented disease progression, the start of new anti-cancer treatment, withdrawal of consent, death, or the end of the study, whichever occurs first.

Each participating site will be responsible for radiological review and confirmation of response as per standard efficacy guidelines. The frequency outlined is the minimum required for study participation. Patients who progress according to the corresponding criteria will receive no further treatment. Patients who respond to the treatment (i.e., CR, PR or SD) may remain on trial. All disease specific assessments are to be completed as applicable to disease type.

- **CTCL:**

CTCL patients will be evaluated as per modified Severity Weighted Assessment Tool (mSWAT) ([Appendix F](#)).^[17] Additionally, CT scan will be done in the CTCL patients with lymph node and visceral involvement. CTCL patients with subcutaneous lesions which cannot be measured by mSWAT will be assessed by change in PET-CT avid lesions. Bone marrow biopsy will be performed in patients with B2 blood involvement. In these patients, Sezary cell count will be quantified by flow cytometry or morphology in blood/bone marrow.

In CTCL patients with other than presumed stage IA disease, or selected patients with limited T2 disease and the absence of adenopathy or blood involvement, CT scans of chest, abdomen, and pelvis alone \pm FDG-PET scan will be done to further evaluate any potential lymphadenopathy, visceral involvement, or abnormal laboratory tests. MRI may be substituted if clinically indicated.

9 STATISTICAL METHOD AND CONSIDERATIONS

This section describes the statistical methods to be used to analyze efficacy and safety. These methods may be revised and updated due to reasons such as regulatory requirements or need for further clarifications. The final analysis plan will be documented in a formal statistical analysis plan (SAP) that must be finalized before database lock. The SAP will include details on how variables will be derived, how missing data will be handled, and how data will be presented as well as the details on statistical methods to be used for safety and efficacy analyses. The final clinical study report will discuss deviations from the SAP, if any.

9.1 General Considerations

Unless otherwise stated, all statistical analyses will be performed using a two-sided hypothesis test at the overall 5% level of significance. The primary efficacy endpoint for the Phase II trial will be evaluated at a one-sided 5% level. No adjustment for Type I error rate will be required because the study has only one primary endpoint with one comparison. P-values will be rounded to three decimal places. If a p-value is less than 0.001 it will be reported as “<0.001”.

Continuous data will be described using the following descriptive statistics: n, mean, median, minimum and maximum. Data will be displayed in all listings sorted by phase, group and patient number. When count data are presented, the percentage will be suppressed when the count is zero in order to draw attention to the non-zero counts. A row denoted “Missing” will be included in count tabulations where necessary to account for dropouts and missing values. Unless otherwise specified, the denominator for percentages will be the number of patients with a non-missing assessment in a given treatment group within the analysis population of interest.

All statistical analyses will be performed using SAS 9.1 or higher.

9.2 Determination of Sample Size

Part 1: In Dose Escalation, three patients per cohort are considered appropriate for the assessment of overall safety and tolerability and for providing adequate confidence for dose escalation. No formal sample size and power analysis is done. Accordingly, total 2-18 patients will be enrolled in 3 escalating cohorts unless additional dose levels are required to reach MTD/ optimal dose. Optimal dose will be determined by the SRC.

Part 2: Total 24 patients with relapsed/refractory TCL will be enrolled in two groups (12 patients in each group). Twelve patients per group is considered appropriate for assessment of preliminary anti-tumor activity of the combination. However, the SRC may modify the sample size due to unforeseen clinical situations.

9.3 Study Population

The following 3 analysis populations are planned for this study:

- Modified Intent-to-Treat Population (mITT): the mITT is the primary efficacy analysis population and will include data from all patients who received at least 1 dose of study medication and provide at least 1 post-baseline efficacy assessment.
- Per-Protocol (PP) Population: the PP Population is a subset of the modified Intent-to-Treat Population and will include patients without major protocol deviations.
- Safety Population: The Safety Population will include all subjects who receive at least 1 dose of the study drug.

Membership in the analysis populations will be determined before database lock.

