1.1.2 Summary of Clinical Evaluation

To date, Tenalisib has been evaluated in four clinical trials:

1. A Phase I Dose Escalation Study Evaluating the Safety and Efficacy of RP6530, a dual PI3K δ/γ inhibitor, in Patients with Relapsed or Refractory Hematologic Malignancies (European study: Protocol Number RP6530-1301) Status: Completed
2. A Phase I/Ib, Dose Escalation Study to Evaluate Safety and Efficacy of RP6530, a dual PI3K δ/γ inhibitor, in Patients with Relapsed or Refractory T-cell Lymphoma (US study: Protocol number RP6530-1401). Status: Recruitment completed. Study Ongoing
3. An open label, randomized, single dose, crossover study to evaluate food effects on relative bioavailability of RP6530 administered in fasting and fed conditions in healthy volunteers (Food effect study, Protocol no: RP6530-1501). Status: Completed
4. An Open label, Phase I/II study to evaluate the safety and efficacy of RP6530, a novel PI3K δ/γ dual inhibitor given in combination with an anti-PD-1 therapy, Pembrolizumab in adult patients with relapsed or refractory Classical Hodgkin's lymphoma (cHL). Status: Ongoing and currently recruiting.

- **Safety:**

In RP6530-1401 study, a total of 58 patients were treated at 200 mg BID (n=4), 400 mg BID (n=4), 800 mg BID (Fasting) (n=44) and 800 mg BID (Fed) (n=6) in both dose escalation and dose expansion cohorts. Tenalisib demonstrated acceptable safety and tolerability profile up to 800 mg BID (fasting). Tenalisib 800 mg BID (Fasting) was considered as MTD dose in patients with T-cell lymphoma. Majority of AEs include transaminitis, skin rash. Treatment related Grade ≥ 3 includes AST/ALT elevation (n=12), rash (n=4), hypophosphatemia (n=2), neutropenia (n=1), INR Increase (n=1), sepsis (n=1), pyrexia (n=1), diplopia secondary to neuropathy (n=1), drug reaction (n=1), and bacteremia (n=1). Treatment related SAE reported were pyrexia (n=1), raised INR (n=1), sepsis (n=1), diplopia secondary to neuropathy (n=1), drug reaction (n=1) and bacteremia (n=1).

- **Pharmacokinetics:**

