In RP6530-1401 study, at the 200 mg dose, AUC_{0-t} and C_{max} were 3713.94 h*ng/mL and 1463.57 ng/mL at C1D1 respectively; corresponding levels at C2D1 were 3985.52 h*ng/mL and 1781.24 ng/mL. Similarly, at the 800 mg dose (fed), AUC_{0-t} and C_{max} were 13204.17 h*ng/mL and 2988.66 ng/mL at C1D1 respectively; corresponding levels at C2D1 were 12737.21 h*ng/mL and 3234.50 ng/mL. At the 800 mg dose (fasting), AUC_{0-t} and C_{max} were 14033.67 h*ng/mL and 4174.71 ng/mL at C1D1 respectively; corresponding levels at C2D1 were 13210.24 h*ng/mL and 3395.28 ng/mL. Based on C_{max} and AUC, dose proportionality was observed up to the 800 mg dose. Upon increasing doses, no changes in T_{max} were observed and while changes in $T_{1/2}$ were observed, steady state PK parameters of Tenalisib as determined on C2D1 revealed no accumulation.

- **Efficacy:**

In RP6530-1401 study, response assessments of the thirty-five evaluable patients receiving at least two cycles of Tenalisib showed an ORR of 46% (16/35 patients) out of which 3 (9%) were CR and 13 (37%) were PR. Eleven patients showed stable disease (31%). Indication specific analysis showed an ORR of 47% (7/15, 3 CR, 4 PR) in PTCL and 45% (9/20, 9 PR) in CTCL. Effect of RP6530 on associated correlative markers in PTCL (sIL-2R and CD30) and CTCL (IL-31, IL-32 α , and CTACK) patients that were either a CR, PR, or SD on C3D1 showed decreased plasma concentrations of markers with the reductions being most pronounced for CD30 (57%) and IL-31 (33%) in the respective patient populations.^[6]

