### 7.3 Modified Intent-to-Treat Population (mITT) Analysis Set

*The mITT is the primary efficacy analysis population and will include data from all patients who received at least 1 dose of study medication and provide at least 1 post-baseline efficacy assessment.*

Note: In order to offer sufficient time for assessing the effectiveness of the study medications, patients who provide the post-baseline efficacy assessment; at least on Cycle 3 Day 1 or are discontinued from study at Cycle 3 Day 1 shall be evaluated for mITT analysis set.

Programmatically, if the patient received at least 1 dose of study medication and have provided at least Cycle 2 Day 22 efficacy assessment, then he/she will be qualified for mITT analysis set.

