## **10. Statistical Analysis**

*Unless otherwise stated, all statistical analyses will be performed using a two-sided hypothesis test at the overall 5% level of significance.*

*Data will be displayed in all listings sorted by phase, group and patient number. When count data are presented, the percentage will be suppressed when the count is zero in order to draw attention to the non-zero counts. A row denoted “Missing” will be included in count tabulations where necessary to account for dropouts and missing values. Unless otherwise specified, the denominator for percentages will be the number of patients with a non-missing assessment in a given treatment group within the analysis population of interest.*

All the patient data including, demographics, medical history, prior/concomitant medications, safety data (where appropriate) and efficacy data will be summarized by following two modes of representation:

1. Dose Escalation (Cohort 1, Cohort 2, Cohort 3, All Cohorts), Dose Expansion (Group 1, Group 2, Both Groups) and Overall.
2. PTCL, CTCL and Overall

All statistical analyses will be performed using SAS 9.4 or higher.

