### 10.5.3 Best Overall Response (BOR)

It is the best response, as assessed and confirmed by site PI, from the start of the treatment until disease progression or discontinuation from the study.

This data will be summarized using frequency and percentage for CR, PR, SD, and PD, as reported in the CRFs for overall subjects. This data will also be listed.

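### ORR and DCR are planned only in patients with a post-baseline efficacy assessment, so treated patients who are never assessed drop out of the denominator and both rates are biased upward

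*Protocol*

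**What the plan says.** - **Efficacy population.** Protocol 9.3 makes the mITT the primary efficacy set and limits it to "all patients who received at least 1 dose of study medication and provide at least 1 post-baseline efficacy assessment". The per-protocol set is a subset of it. Protocol 8.1 uses the same idea: patients with a baseline evaluation and "at least one post-treatment efficacy evaluation will be considered evaluable for response".
- **SAP version.** SAP 7.3 repeats the definition and adds a programming rule under which a patient qualifies "if the patient received at least 1 dose of study medication and have provided at least Cycle 2 Day 22 efficacy assessment".
- **Sets used.** SAP 10.5 names mITT and PP for all efficacy analyses and no other set.
- **ORR and DCR.** SAP 10.5.1 gives frequencies, percentages and exact binomial 95% intervals. It states no denominator of its own and does not say how an unassessed patient is counted.
- **Percentages in general.** Unless otherwise specified, "the denominator for percentages will be the number of patients with a non-missing assessment" (SAP 10; the same rule is in Protocol 9.1). The same paragraph allows a row for missing values in count tables where necessary.
- **Best overall response (BOR).** SAP 10.5.3: "This data will be summarized using frequency and percentage for CR, PR, SD, and PD".
- **Contrast with safety.** SAP 10.6.2 takes adverse event percentages over the whole safety set, that is, everyone who received at least one dose.

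**The concern.** Membership of the efficacy set depends on something that happens after treatment starts. A treated patient who dies, withdraws or stops before any efficacy assessment is removed from the ORR instead of being counted as a treatment that did not produce a response.

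Some loss of this kind is foreseeable. The first scheduled response assessment is about 8 weeks in (Protocol 8.2). Eligibility admits ECOG 2 and asks for a life expectancy of 3 months (Protocol 4.1). Protocol 7.6.3 itself provides for withdrawal during Cycle 1 because of progression or withdrawn consent.

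The trial has no control arm, so the ORR and its interval are the main description of anti-tumor activity. With 12 patients per expansion group, each patient removed visibly changes the estimate.

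**Working it through.** **Inputs**
- N = 12 per expansion group, 24 in total (Protocol 9.2, SAP 6).
- Interval method: exact binomial, 95% (SAP 10.5.1).
- m = number of treated patients with no efficacy assessment. The documents give no figure, so 0 to 3 per group is assumed.
- x = number of responders. The plan states no target ORR, so 5 of 12 is assumed.

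The plan has no power calculation or target rate for the expansion, so there is no design figure to reproduce.

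**Direction**
- All-treated rate: x/N, with unassessed patients counted as non-responders.
- Planned rate: x/(N − m), because the m patients are outside the mITT.
- A response cannot be recorded without an assessment, so x is the same in both. The ratio of planned to all-treated is N/(N − m), which is above 1 whenever m > 0. The same ratio applies to DCR, because stable disease also requires an assessment.

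**Size, one group (N = 12, x = 5)**

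| Unassessed m | Planned ORR | Exact 95% CI | Excess over 5/12 |
|---|---|---|---|
| 0 | 5/12 = 41.7% | 15.2 to 72.3 | 0 |
| 1 | 5/11 = 45.5% | 16.7 to 76.6 | 3.8 points |
| 2 | 5/10 = 50.0% | 18.7 to 81.3 | 8.3 points |
| 3 | 5/9 = 55.6% | 21.2 to 86.3 | 13.9 points |

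The ratios are 12/11 = 1.09, 12/10 = 1.20 and 12/9 = 1.33.

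**Size, both groups (N = 24, x = 11, assumed)**
- All treated: 11/24 = 45.8%.
- 2 unassessed: 11/22 = 50.0%, which is 4.2 points higher.
- 4 unassessed: 11/20 = 55.0%, which is 9.2 points higher.

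**Who is lost**

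Under the protocol definition, any one post-baseline assessment keeps a patient in. Protocol 8.2 requires assessment at end of treatment or when progression is suspected, and Protocol 6.12 places the end-of-treatment visit within 7 days of the last dose or discontinuation. The loss is therefore confined to patients with no assessment at all. One gap in that protection is in Protocol 6.12 itself: radiology is waived at end of treatment if done in the previous 28 days. On that wording, a screening scan could satisfy the waiver for a patient who stops in the first weeks.

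**The case against.** The strongest reply is that most early failures are assessed. A patient who progresses clinically or stops for toxicity should have an end-of-treatment or clinically indicated assessment. For PTCL, Protocol 8.2 continues imaging until progression, new treatment, withdrawal of consent, death or study end. This largely stands. A reader might infer that early progressors and toxicity stops as a class leave the ORR; under the protocol definition they do not. SAP 7.3's Cycle 2 Day 22 rule is narrower and would not admit an earlier end-of-treatment scan. That conflict with the protocol is a separate matter, and the present point does not depend on it.

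Four further limits also stand.

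- **The non-missing denominator is not a second, equal source of bias.** Everyone in the mITT already has an assessment, so within that set the rule can remove at most patients whose assessments were all unevaluable.
- **The BOR table is not without a place for missing patients.** SAP 10 allows a missing row where necessary. However, patients outside the mITT never reach that row, and the denominator rule leaves it out of the percentages.
- **The earlier Tenalisib study does not measure this effect.** Protocol 1.1.2 reports that "a total of 58 patients were treated" and that "thirty-five evaluable patients receiving at least two cycles of Tenalisib showed an ORR of 46"%. It is tempting to set 16/35 = 46% against 16/58 = 28%. But the 35 had to have received two cycles, which is a different filter, the study was ongoing, and the two counts are not shown to share a data cut.
- **No decision depends on the ORR.** It is a secondary endpoint, SAP 9.1 tests no hypothesis, and no formal comparison with the published romidepsin rates (26% and 35%, Protocol 1.2) is planned. Protocol 9.1 mentions a one-sided 5% evaluation of a primary efficacy endpoint but names no such endpoint and no reference rate.

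Finally, SAP 10.1 reports the size of each population set and SAP 14 lists responses, so a reader could rebuild an all-treated rate. That helps transparency, but it does not make the figure or its interval prespecified.

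**Conclusion.** The concern holds for treated patients with no efficacy assessment at all. Both planned efficacy sets exclude them, no all-treated ORR or DCR is planned, and no rule counts them as non-responders. The direction of the bias is certain by arithmetic. Its size is not known: it is zero if every treated patient is assessed, and with 5 responders in a group of 12 it is about 4, 8 or 14 points for 1, 2 or 3 unassessed patients. Those counts are assumptions.

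The shifts are smaller than the sampling uncertainty at this size (the interval for 5/12 spans 15% to 72%), but the planned interval is computed on the reduced denominator and does not allow for the exclusion. What is affected is the reported estimate and its interval, not a go/no-go rule. Duration of response is unaffected, because it is confined to responders. The point should be corrected before database lock, but it does not threaten the primary safety objective.

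**What to change.** In SAP 7.3 and 10.5.1:

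1. Report ORR and DCR with exact 95% intervals over all patients who received at least one dose (the existing Safety Population). Count no assessment, not evaluable and not done as non-response. Make this the main estimate, with mITT and PP as supportive. At minimum, prespecify it as an analysis shown beside mITT and PP.
2. State in SAP 10 that the non-missing denominator rule does not apply to ORR, DCR or BOR.
3. In SAP 10.5.3, show not-evaluable and not-done patients in the BOR table, within that all-treated denominator.

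No new data or patients are needed. SAP 2 says the SAP may modify the protocol's plans, so the change can be made there. If the sponsor prefers to leave the primary efficacy population in Protocol 9.3 untouched, the side-by-side version in item 1 does so. The cost is SAP wording, one extra table run, and an ORR that may be somewhat less favourable.
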